## **Protocol Summary**

This document represents the protocol summary for the study on human subjects. The study will be carried out in accordance with ICH GCP, National Standard of the Russian Federation GOST 52379-2005 "Good Clinical Practice", World Medical Association Declaration of Helsinki, relevant requirements of the regulatory authorities as well as the study procedures.

### **Title of Study**

Multicenter double-blind placebo-controlled randomized parallel-group clinical study of efficacy and safety of MMH-MAP in the treatment of mild cognitive impairment in subjects in early rehabilitation period of ischemic stroke.

**Phase:** III

**Sponsor:** Company «MATERIA MEDICA HOLDING», Moscow, Russia

**Protocol No.** MMH-MAP-001

### **Objective of the study**

- To evaluate efficacy of MMH-MAP in the treatment of mild cognitive impairment in subjects in early rehabilitation period of ischemic stroke.
- To evaluate the safety of MMH-MAP in the treatment of mild cognitive impairment in subjects in early rehabilitation period of ischemic stroke.

### **Endpoints**

#### **Primary endpoint**

1. Proportion of subjects with improved cognitive functions (MoCA  $\geq$  +1) after 24-week therapy compared to baseline.

#### **Secondary endpoints**

1. Change in MoCA scores after 24 weeks of treatment.
2. Percentage of patients with improved performance in activities of daily living (total Barthel Index score + 5 or more) after 24 weeks of treatment.
3. Changes in Barthel index for activities of daily living after 24 weeks of treatment.
4. Change in SS-QOL total score after 24 weeks of therapy.
5. Therapeutic effect and adverse event values and CGI-EI scores after 24 weeks of treatment.
6. Changes in intensity of cognitive disorders (MoCA) in follow-up period (24–28 weeks).
7. Changes in Barthel index for activities of daily living in follow-up period (24–28 weeks).
8. Changes in SS-QOL in follow-up period (24–28 weeks).

## **Safety assessment**

- Presence and nature of adverse events during the therapy, their intensity (severity), relation to the product, outcome.
- Changes in vital signs.
- Percentage of patients with clinically relevant laboratory abnormalities.

## **Study design**

Design – multicenter double blind placebo-controlled randomized parallel-group clinical study.

The study patients are subjects of either gender, aged 45-80 years old, after an ischemic stroke within 3-6 months prior to enrollment and confirmed by neuroimaging, having mild cognitive impairment.

After the patients provide signed Participant Information Sheet and Informed Consent, they will be interviewed for complaints and medical history and undergo physical examination and laboratory tests. The doctor will rate the severity of patients' cognitive impairments on the Mini Mental State Examination (MMSE) scale and Montreal Cognitive Assessment (MoCA) scale, assess their performance in activities of daily living on the Barthel Index scale, and administer the Stroke Specific Quality of Life Scale (SS-QOL) questionnaire. Eligible participants will have to have moderate cognitive impairments (MMSE score - at least 21 and MoCA - less than 26). Therapy received by patients for their co-morbidities and primary diagnosis will be recorded. All women of childbearing potential will be administered pregnancy tests.

If a patient meets all inclusion criteria and does not have any exclusion criteria at Visit 1, he/she is randomized to one of the two groups: group 1 will receive MMH-MAP at 2 tablets twice daily; group 2 will receive Placebo using the study product dosing regimen. The total duration of follow-up and treatment will be 28 weeks, which will include 5 additional visits.

At Visit 2 (Week 4±7 days), the doctor records patients' complaints and physical examination data, reviews the progress of study and basic and concomitant therapy, and assesses treatment safety and patient compliance with treatment.

At Visit 3 (Week 8±7 days), Visit 4 (Week 16±7 days), and Visit 5 (Week 24±7 days), the doctor assesses patients' cognitive impairments (MoCA) and performance in activities of daily living (the Barthel Index). The patients complete the SS-QOL questionnaire.

At Visit 5 (Week 24±7 days), the doctor will additionally complete the Clinical Global Impression Efficacy Index (CGI-EI) scale and collect samples for laboratory testing. The patient stops taking the study drug.

After four weeks following the end of study therapy patients complete a follow-up visit –Visit 6 (Week 28±7 days). The patients are interviewed for complaints and undergo physical

examination, with a check on their concomitant and primary therapies as well as on the safety of study treatment. The doctor assesses patients' cognitive impairments (MoCA) and performance in activities of daily living (the Barthel Index) and administers the SS-QOL questionnaire.

The total length of the observation period will be 28 weeks.

During the study, symptomatic therapy and therapy for underlying chronic conditions are allowed with the exception of the drugs indicated in the section "Prohibited Concomitant Treatment".

## **Inclusion and exclusion criteria**

### ***Inclusion criteria***

1. Patients of either sex, aged 45 to 80 years old inclusively.
2. Patients with a history of one stroke sustained 3 to 6 months prior to study entry and confirmed by neuroimaging.
3. Patients with cognitive impairment (MoCA score < 26).
4. Patients with moderate performance in activities of daily living (Barthel score = 61-80).
5. Agreement to use a reliable method of birth control for the duration of the study (men and women of reproductive potential)
6. Availability of signed patient information sheet (Informed Consent form) for participation in the clinical trial.

### ***Exclusion criteria***

1. Patients with a history of subarachnoid/parenchymatous/ventricular hemorrhage, brain neoplasm, or any other condition which has caused neurological dysfunction.
2. History of central nervous system (CNS) disorders, including:
  - inflammatory diseases of the CNS (G00-G09)
  - systemic atrophies primarily affecting the CNS (G10-G13)
  - extrapyramidal and movement disorders (G20-G26)
  - other degenerative diseases of the nervous system (G30-G32)
  - demyelinating diseases of the CNS (G35-G37)
  - epilepsy (G40-41)
  - polyneuropathies and other disorders of the peripheral nervous system (G60-64), with marked movement and/or sensory impairments that cause movement disorders
  - diseases of neuromuscular junction and muscle (G70-73)
  - hydrocephalus (G91)
  - compression of brain (G93.5).
3. Dementia (20 or less on the MMSE score).

4. Speech disorders affecting investigator-patient communication.
5. Prior diagnosis of heart failure defined by the New York Heart Association classification (1964) as IV Functional Classification or poorly treated hypothyroidism or diabetes mellitus.
6. Patients having unstable angina or myocardial infarction in the past 6 months.
7. History/suspicion of oncology of any location (except for benign neoplasms).
8. Any other co-morbidity which, in the opinion of the investigator, may affect patient participation in the clinical trial.
9. Patients allergic to/intolerant of any components of the study treatment.
10. Patients with hereditary lactose intolerance.
11. Malabsorption syndrome, including congenital or acquired lactase deficiency (or any other disaccharidase deficiency) and galactosemia.
12. Pregnancy, breast-feeding or unwillingness to use birth control during the study.
13. Patients who, from the investigator's point of view, will not comply with the observation requirements of the study or adhere to study drug dosing regimens.
14. Patients with a history of non-adherence to medication; mental disorder (except for cognitive deficits); or alcoholism or abuse of psychoactive substances, which, in the investigator's opinion, will compromise compliance with study procedures.
15. Patients who have used medications listed in 'Prohibited Concomitant Treatment' in the past week.
16. Participation in other clinical trials in the previous 3 months.
17. Patients who are related to any of the on-site research personnel directly involved in the conduct of the trial or are an immediate relative of the study investigator. 'Immediate relative' means husband, wife, parent, son, daughter, brother, or sister (regardless of whether they are natural or adopted).
18. Patients who work for MATERIA MEDICA HOLDING (i.e. the company's employees, temporary contract workers, appointed officials responsible for carrying out the research or immediate relatives of the aforementioned).

### **Criteria for Withdrawal or Termination**

1. Screening failure.
2. Inability or patient's refusal to comply with the protocol requirements.
3. Necessity in medications prohibited within the study.
4. An adverse event requiring discontinuation of the study product.
5. Eligibility error.
6. Pregnancy.

7. Patient's decision to complete the study ahead of schedule due to lack of the therapy efficacy or any reasons.
8. Enrollment of the subject into another clinical study.
9. Cases not stipulated in the protocol where the investigator decides that further participation may harm the patient.
10. Unblinding.

### **Number of subjects**

It is planned to include 276 subjects, which is expected to yield at least 220 patients completing all protocol procedures.

### **Interim analysis**

Two interim analyses are scheduled in the study: involving 15% and 30% subjects recruited. Type 1 error distribution is in accordance with O'Brien-Fleming alpha spending function, type II - according to Pocock test. Early study termination is possible both due to acceptance and rejection of null hypothesis.

### **Treatment**

#### **Group 1**

**Name of the medicinal product:** MMH-MAP

**Active ingredient:** Affinity purified antibodies to S-100 brain protein – 0.006 g, modified. C200 dilution.

**Excipients:** Lactose monohydrate - 0.267g

Microcrystalline cellulose - 0.030 g

Magnesium stearate - 0.003 g

**Method of administration:** Tablet for oral use. Dose per administration: 2 tablets. 2 tablets twice daily (4 tablets/day). The tablets should be held in mouth without chewing until complete dissolution.

**Dosage form:** Tablets.

**Description:** Flat cylinder-shaped scored beveled edge white to off-white tablets.

**Storage conditions:** At temperature  $\leq 25$  °C.

#### **Group 2**

**Name of the medicinal product:** Placebo

**Active ingredient:** No

**Excipients:** Lactose monohydrate - 0.267 g

Microcrystalline cellulose - 0.030 g

Magnesium stearate - 0.003 g

**Method of administration:** Tablet for oral use. Dose per administration: 2 tablets. 2 tablets twice daily (4 tablets/day). The tablets should be held in mouth without chewing until complete dissolution.

**Dosage form:** Tablets.

**Description:** Flat cylinder-shaped scored beveled edge white to off-white tablets.

**Storage conditions:** At temperature  $\leq 25$  °C.

***Treatment duration***

MMH-MAP/Placebo treatment duration is 24 weeks.

***Observation period***

The total length of patient observation is 28 weeks (screening + randomization – up to 1 day, treatment – 24 weeks, follow-up – 4 weeks).

***Symptomatic (Standard) treatment***

Throughout the study the subject will receive therapy for the underlying disease including therapy designed for secondary prevention of stroke and other vascular events except for the medicinal products referred to in "Prohibited concomitant therapy".

1. Antihypertensive products.
2. Angiotensin-converting enzyme (ACE) inhibitors.
3. Angiotensin II receptor antagonists.
4.  $\beta$ -adrenoblockers or  $\alpha$ - and  $\beta$ -adrenoblockers.
5. Calcium antagonists (except for nimodipine).
6. Diuretics (thiazide, aldosterone receptor antagonist).
7. Antiplatelets (acetylsalicylic acid, clopidogrel, dipyridamol, ticlopidine, ticagrelor).
8. Anticoagulants.
9. Statins.
10. Antidiabetic drugs.
11. Other agents except for those referred to as prohibited ones.

***Prohibited concomitant therapy***

Within 1 week prior to enrollment and during the study (beginning from signing patient information sheet and informed consent form and initiation of screening) subjects are not allowed to receive any medications that may affect mental and emotional status (parenthesized is the ATC group):

1. Peripheral vasodilators (ATC group – C04) including nicotinic acid and its derivatives; purines (xantinol nicotinate, pentoxifylline), ergot alkaloids (nicergoline, alpha-

[figure not shown]
dihydroergocryptine + caffeine), other vasodilators (vincamine, bencyclane, naftidrofuryl), papaverine, etamivan+etophylline+hexobendine.

2. Calcium channel blockers – nimodipine (C08CA06), instenon (C01EX).
3. Muscle relaxants (M03).
4. Anticholinergic agents (N04A).
5. Dopaminergic agents (N04B).
6. Actovegin (B06).
7. Psycholeptics (N05), including anxiolytics (tranquilizers), hypnotics and sedatives.
8. Psychoanaleptics (N06), including antidepressants, psychostimulants and nootropics including:
  - pyrrolidine derivatives (racetams) – piracetam, etiracetam, aniracetam, etc.;
  - dimethylaminoethanol derivatives (acetylcholine precursors) - deanol aceglumate, meclofenoxate;
  - pyridoxine derivatives - pyritinol, biotredin;
  - GABA derivatives and analogues – gamma-aminobutyric acid, nicotinoyl gamma-aminobutyric acid, gamma-amino-beta-phenylbutyric acid hydrochloride, hopantenic acid, calcium gamma-hydroxybutirate;
  - ginkgo biloba;
  - neuropeptides and their analogues - methionyl-glutamyl-histidyl-phenylalanyl-propyl-glycyl-proline;
  - aminoacids and substances affecting excitatory amino acid system – glycine, pyrodoxine+threonine;
  - derivatives of 2-mercantobenzimidazole – ethylthiobenzimidazole hydrobromide;
  - idebenon;
  - vinpocetine;
  - polypeptides and organic composites - bovine cortical polypeptides, cerebrolysin;
  - memantine (N06DX01).
9. Other nervous system drugs (N07) including:
  - parasympathomimetics (N07A);
  - antivertigo preparations (N07C);
  - other nervous system drugs (N07X).
10. Substances of other pharmacological group with a nootropic ingredient including:
  - general tonic agents and adaptogens – ginseng, melatonin, lecithin, acetylaminosuccinic acid etc.;

- antihypoxants and antioxidants – ethylmethylhydroxypyridine succinate, citicoline, vitamin E, etc.;
- metabolic agents.

11. Any unauthorized product and/or vaccine.
12. Drugs that previously caused allergic reactions in patient.

### Study design scheme

### Schedule of study procedures

Procedure/Visit	Visit 1 Screening, Randomization (Day 1)	Visit 2 (Week 4±7 days)	Visit 3 (Week 8±7 days)	Visit 4 (Week 16±7 days)	Visit 5 (Week 24±7 days)	Visit 6 (Week 28±7 days)
Informed consent	+					
Registration patient in IVRS and assignment of a personal code	+					
Collection of complaints	+	+	+	+	+	+
Medical history	+					
Concomitant conditions and diseases	+					
Physical examination	+	+	+	+	+	+
Evaluation of vital signs (HR, RR, BP) *	+	+	+	+	+	+
Recording therapy for concomitant diseases	+	+	+	+	+	+

Recording basic therapy	+	+	+	+	+	+
Inclusion/exclusion criteria	+					
Randomization	+					
Filling MMSE	+					
Filling MoCA	+		+	+	+	+
Filling Barthel scale	+		+	+	+	+
Filling SS-QOL	+		+	+	+	+
Laboratory tests 	+				+	
Pregnancy test	+					
Drug issue	+	+	+	+		
Study drug accountability, compliance assessment		+	+	+	+	
Clinical Global Impression assessment (CGI-EI)					+	
Evaluation of treatment safety	+	+	+	+	+	+
Visit completion	+	+	+	+	+	+
Suggested duration of the subject's participation in the study						+

\*HR - heart rate; RR - respiration rate; BP - blood pressure

### ***Evaluation of sample size***

The sample size was assessed in accordance with the following rules and assumptions:

1. Statistical assumptions
  - 1.1 the power of statistical tests ' $P = (1 - \beta)$ ' is 80% (the probability of correct rejection of the null hypothesis is 0.8)
  - 1.2 the probability of type 1 error 'a' is less than 5% (the probability of false acceptance of the alternative hypothesis is less than 0.05);
  - 1.3 statistical criteria of intergroup comparisons will be two-sided, equivalence criterion - one-sided;

---

 Holder of license: OOO "NPF "Materia Medica Holding", No. 70100045.

- 1.4 calculation of sample size will be based on the assumptions on the expected effect declared in the primary efficacy criterion of the protocol;
- 1.5 ratio between sample sizes of MMH-MAP and Placebo sample sizes is 1:1 (1 MMH-MAP subject per 1 Placebo subject);
- 1.6 statistical hypotheses - null and alternative hypotheses on the difference between test product and placebo under the dosing regimen used:

$$H_0: \Theta_1 - \Theta_2 = 0$$

$$H_a: \Theta_1 - \Theta_2 \neq 0$$

where  $\Theta_1$  is frequency of the claimed event in MMH-MAP group, a  $\Theta_2$  is frequency of the claimed event in Placebo group;

- 1.7 calculation of sample size for statistical criteria was made using the following program code:

```
Proc seqdesign errspend
```

```
Design nstages = 3
```

```
Info = cum (0.15,0.3,1)
```

```
Method (alpha) = UNI (rho = 0.5 tau = 0)
```

```
Method (beta) = UNI (rho = 0 tau = 0)
```

```
Stop = both
```

```
Alpha = 0.05
```

```
Beta = 0.2
```

```
Samplesize model = twosamplefreq (test = PROP nullprop = 0.4 prop = 0.6)
```

```
Run;
```

- 1.8 terminal sample size will be determined using the formula:

$$N_T = N_{PP} / (1 - R_w)$$

where  $N_T$  – terminal sample size;  $N_{PP}$  – result of calculation in c. 1.7 i.e.

scheduled number of subjects completing the study per protocol;  $R_w$  – withdrawal rate.

## 2. Assumptions on expected clinical study effects:

Proportion of subjects with improved cognitive function (MoCA  $\geq$  +1) after 24-week therapy with MMH-MAP is expected to be no less than 60%, Placebo – no more than 40%.

Therefore, group size needed to compare test product and placebo will be **110** subjects for each group. Given potential withdrawal of at least 20% subjects (**Rw=0.2**) during the study for various reasons, at least **276** subjects will be required to sign informed consent, with **138** subjects per group (see cl. 1.8).

***Statistical criteria***

All statistical calculations will be made using two groups of statistical criteria:

- parametric - to obtain effective estimates for random parameters in case the relevant conditions of method/model applicability are not violated (e.g. sphericity, normality, risk proportionality, etc.)
- nonparametric – in all other cases.

***Parametric criteria***

The application of parametric criteria will be accompanied by a check of models for applicability (e.g. Kolmogorov-Smirnov test, Shapiro-Wilk test).

The following parameters and approaches are to be used:

1. To evaluate the differences in continuous variables obtained in one group at two different visits – Student’s test for matched samples.
2. To evaluate time changes in parameters compared - analysis of variance (ANOVA) or modified repeated measures covariance (ANCOVA).
3. In case of multiple comparisons of the groups various corrections for multiplicity will be used, e.g. Dunnett, Tukey, Scheffe, Holm adapted test, etc.
4. Generalized Linear Models and/or Mixed Linear Models will be used in case of abnormal data distribution.
5. Selection of the type of distribution, specification of factor and covariance structures of the model will be made using fit-statistics such as AIC (Akaike information criterion).

The following SAS software programs are supposed to be applied to the above listed tests and techniques:

- UNIVARIATE – normality verification of the distributions under comparison
- CORR, MEANS – calculation of descriptive statistics
- TTEST – Student’s test with all modifications
- GLM – generalized linear models for analysis of time changes (ANOVA, ANCOVA)
- GENMOD – generalized linear models
- MIXED – mixed linear models.

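### For the 24-week change endpoints, fit statistics may choose the model's factors, so the effect estimated need not be the Week 24 effect and nominal error and coverage are not guaranteed

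*Combined protocol and SAP*

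**What the plan says.** The rule is item 5 under Parametric criteria: "Selection of the type of distribution, specification of factor and covariance structures of the model will be made using fit-statistics such as AIC". It covers three choices: distribution, factors and covariance. AIC is given only as an example, so the criterion itself is open.

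The Statistical Analyses section gives no list of candidate models, no requirement that treatment terms stay in, no named contrast, no blinding of the selection and no fallback model.

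Secondary endpoints 1, 3 and 4 are the changes in MoCA, Barthel and SS-QOL at 24 weeks. The schedule of procedures has these scales completed at baseline, at Weeks 8, 16 and 24 on treatment, and at Week 28 in follow-up. Item 2 of Parametric criteria sends changes over time to ANOVA or repeated-measures ANCOVA, and the procedure list includes GLM, GENMOD and MIXED.

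On error rates, Evaluation of sample size (1.2) says "the probability of false acceptance of the alternative hypothesis is less than 0.05", and 1.3 adds that "statistical criteria of intergroup comparisons will be two-sided". By 1.4 that calculation rests on the primary criterion. Data presentation promises confidence intervals but gives no level.

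**The concern.** In a model with several visits, the treatment-by-visit term decides which effect is estimated. With it, the Week 24 difference is estimated separately. Without it, the model gives one treatment effect averaged over Weeks 8, 16 and 24. If a fit statistic on the outcome data makes that choice, the data select the question and the same data then answer it as though it had been fixed.

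Two things are at stake for the MoCA, Barthel and SS-QOL change endpoints. The reported effect may not be the Week 24 effect that the endpoints define. P-values and intervals computed as if the model had been fixed may also be somewhat optimistic, most of all when the effect changes between Week 8 and Week 24.

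**Working it through.** **Size per arm.** The plan states 110 completers per group and 276 in total. Its three-stage design (information 0.15, 0.30, 1; O'Brien-Fleming alpha, Pocock beta) gives a drift of 3.023. The per-group size is then 0.48 × 3.023² / 0.2² = 109.6, so 110, where 0.48 = 0.6 × 0.4 + 0.4 × 0.6. Allowing for withdrawal, 110 / 0.8 = 137.5, so 138 per group and 276 in total. The plan's figures are reproduced and do not depend on item 5. Only the 110 is carried forward.

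**Inputs from the plan.** 110 per arm, three on-treatment visits, two-sided tests.

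**Assumptions, not in the plan.** Complete data, variance treated as known, visit correlation ρ from 0.4 to 0.8, a nominal two-sided 5% test and 95% interval, AIC from maximum-likelihood fits, and a choice only between models with and without treatment-by-visit. The effect profiles are also assumed.

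**Selection rule.** With three visits, treatment-by-visit has 2 degrees of freedom. AIC charges 2 per parameter, so the term is kept if the likelihood-ratio statistic exceeds 4. Under the null it is kept with probability P(χ²₂ > 4) = e⁻² = 13.5%.

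**What is tested.** If the term is kept, the Week 24 difference; if dropped, the common effect.
- Standard error of a visit difference: √(2/110) = 0.135 SD.
- Standard error of the common effect under compound symmetry: 0.135 × √((1 + 2ρ)/3), that is 0.105 SD at ρ = 0.4 and 0.126 SD at ρ = 0.8.
- Common effect for a build-up of 0.1/0.2/0.3 SD: 0.20 SD, against 0.30 at Week 24. At ρ = 0.4 the shortfall is 0.10/0.105, nearly one standard error.
- Common effect for a fade of 0.30/0.15/0 SD: 0.15 SD, against 0 at Week 24.

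**Results**, simulated from the joint normal distribution of the three visit differences, compound symmetry, ρ = 0.4 to 0.8 (the worse end is ρ = 0.4; repeat runs differ by about 0.1 point):

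| True effect, Weeks 8/16/24 (SD) | Quantity | Result |
|---|---|---|
| 0/0/0 | two-sided rejection | 5.4–6.2% |
| 0.1/0.2/0.3 | interaction dropped | 28–63% |
| 0.1/0.2/0.3 | coverage of Week 24 effect | 87–93% |
| 0.2/0.2/0.2 | coverage of Week 24 effect | about 94–95% |
| 0.30/0.15/0 | two-sided rejection | 5.6–14.5% |
| 0.30/0.15/0 | rejection favouring the drug (nominal 2.5%) | 3.0–12.1% |

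AR(1) correlation is somewhat worse: null error reaches about 6.4%, build-up coverage is 86–91%, and fade rejection is 8–19%.

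**The other choices in item 5.** Simulated under the null with 110 per arm and treatment always in the model, type I error was 5.1–5.2% when AIC chose covariate main effects (5 or 8 candidates), 4.8–4.9% when it chose between normal and log-normal, and 4.7–5.3% when it chose among compound-symmetric, AR(1) and unstructured covariance. None of these matters materially for error.

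**The case against.** The strongest reply is that the mechanism is possible but not documented. The plan never mentions treatment-by-visit. Item 4 reserves generalized and mixed models for non-normal data, so item 5 may apply only there. The endpoints are fixed at 24 weeks, and a single-time-point analysis has no visit interaction to drop. The low coverage and the excess rejection come from chosen profiles; with a constant effect, coverage is nearly nominal.

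Much of this stands, and it limits the size of the point. It does not remove it. Item 5 gives factor choice to fit statistics, the plan lists repeated-measures methods for changes over time, and no sentence fixes the treatment terms or the contrast. A single-time-point analysis would avoid the problem, but the plan does not commit to one.

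Several stronger readings are tempting and not supported:
- **That the primary result is affected.** The primary hypothesis is a fixed difference of two proportions, and tests for 2×2 tables are listed outside item 5. No named test is tied to the primary endpoint, but that is a separate gap.
- **That a stated 5% and a stated coverage fail.** The 5% belongs to the primary comparison, and no interval level is given.
- **That error reaches about 9.3%.** That is 5% + 0.865 × 5%, and it counts a significant interaction as an efficacy success. The plan makes no such test.
- **That error reaches 13–18% if treatment-by-covariate terms are selectable.** Those figures need a joint test, or any significant treatment term, to count as success. The plan says neither.
- **That the AIC comparison is itself invalid because MIXED would be fitted by REML.** The plan states no estimation method and also lists GENMOD.

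**Conclusion.** The point holds for the secondary change endpoints in MoCA, Barthel and SS-QOL. Their models are not fixed, and the written rule allows the data to decide whether the reported effect is the Week 24 difference or an average over Weeks 8 to 24. Nominal error and coverage are therefore not guaranteed; the documents do not show that they fail.

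The harm is modest under the null, 0.4 to 1.2 percentage points above 5% with compound symmetry. It is larger when the effect changes over time: coverage can fall to 87%, and an effect that has gone by Week 24 can be declared in the drug's favour in up to 12.1% of trials. These sizes rest on the assumed correlations and profiles and on treatment-by-visit being among the selectable factors. The mismatch with the defined endpoint matters even where error moves little. This should be corrected, but it does not threaten the primary analysis or the sample size.

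**What to change.** Remove factor selection from item 5. For each continuous secondary endpoint at 24 weeks, state one fixed model with treatment, visit, treatment-by-visit and baseline score, and name the Week 24 treatment contrast as the result. Limit AIC to choosing the covariance structure from a set listed in the SAP.

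The change is to SAP wording only; sample size, visits and data collection stay as they are. It costs a few degrees of freedom (two for treatment-by-visit and one for baseline), negligible at about 110 per arm. It also gives up some precision if the true effect is constant over visits: the averaged effect would have a standard error smaller by 1 − √((1 + 2ρ)/3), about 7% at ρ = 0.8 and 22.5% at ρ = 0.4. That is the price of estimating the effect the endpoints define.
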